Overall renal function appears to transiently decrease following nephron sparing surgery in a manner which suggests delayed recovery. As demonstrated in Figure 1, the profile of renal function, as assessed by eGFR, appears comparable for patients managed with and without mannitol based on retrospective data. Overall, the recovery of renal function was very similar in both groups ($p=0.8$ for effect of mannitol from GEE model). The predicted eGFR for a typical patient 2 months after surgery was 62 ml/min/1.73m² both for those given and not given mannitol; at 6 months the respective predicted GFR measurements were 63 and 64 ml/min/1.73m². It is notable that the mannitol group had a lower nadir and recovery of eGFR than the group who did not receive mannitol. In evaluating the open surgical experience in over 850 open partial procedures 34 did not receive mannitol, many of who did not require renal ischemia, limiting our evaluation of this cohort.

[figure not shown]

Figure 1. Population-averaged changes in GFR ($\text{mL}/\text{min}/1.73\text{m}^2$) after partial nephrectomy for patients given mannitol (grey line) and not given mannitol (black line), adjusted for differences in preoperative GFR, age, gender, ASA score, estimated blood loss, and ischemia time. Dashed lines indicate 95% confidence intervals. The histogram shows the number of GFR measurements over time, excluding postoperative measurements taken within two days of surgery that were recorded for all patients.

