4.0 OVERVIEW OF STUDY DESIGN/INTERVENTION

4.1 Design

This study is a prospective randomized double blind placebo controlled trial comparing renal function outcomes in patients undergoing partial nephrectomy for renal tumors. Patients will be randomized in 1:1 fashion to receive mannitol or saline provided intravenously within 30 minutes prior to renal vascular clamping for performing partial nephrectomy.

Patient randomization will be accomplished by the Clinical Research Database (CRDB) once eligible patients have been consented and registered in the Protocol Participant Registration system. Pharmacy will be able to access the requisite information on the CRDB to ensure correct delivery of either mannitol or saline to the treatment or placebo arms respectively. The anesthesiologist, surgeon and patient will be blinded to the intervention.

To avoid any compromise in the blinding process, mannitol input into CASIS will be deferred until after the trial has finished. At this time it will be entered into CASIS by the research assistant.

An interim analysis half way through the trial when 88 patients have eGFR measurements at 6 months. The O'Brien-Fleming stopping boundaries will be used. The significance levels for the interim and final analyses are 0.0031 and 0.049, respectively.

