10.0 EVALUATION DURING TREATMENT/INTERVENTION

This protocol does not require any additional evaluations after the patient is admitted for surgery other than those routinely part of clinical care for a patient undergoing a partial nephrectomy. These will include:

- ASA classification, assigned by the anesthesiologist
- Deep venous thrombosis prophylaxis per standardized pathway

- Type of anesthesia: general, epidural, combination
- Duration of anesthesia and of surgery
- Duration of warm or cold ischemia time
- Estimated blood loss
- Use of intraoperative fluids (crystalloid, colloid, blood products)
- Postoperative day 1 and postoperative day 2 serum creatinine measurement. For patients discharged before post-operative day 2, serum blood testing will be ordered as an outpatient test.
- Follow up visit serum creatinine measurements (6 weeks +/- 4 weeks and 6 months +/- 2 months)
- 6 month +/- 2 months follow up radio nuclear scintigraphy renal scan, which is a routine postoperative investigation for patients who have undergone a partial nephrectomy.
- Patients may be concurrently enrolled on protocol 89-076 for collection of tissue and blood for tissue banking.

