12.0 CRITERIA FOR THERAPEUTIC RESPONSE/OUTCOME ASSESSMENT

As an intent-to-treat study, patients will be evaluated for the primary endpoint if they are registered on study, brought to the operating room for surgery, and begin anesthesia for the procedure. Because the role of mannitol as a protective agent in regard to kidney function is not entirely clear and its mechanism of action may be mediated through its effects on the contralateral kidney, all patients will be evaluated for the primary endpoint even if the ipsilateral kidney is not clamped during the procedure. If the surgery is aborted for any reason before attempted excision of the mass or if intravenous infusion fails for any reason the patient will be dropped from the study and replaced. Based on past experience these issues are rare events.

Estimated glomerular filtration rate (eGFR) will be estimated according to the CKD-EPI formula.

Perioperative complications are defined as any complication graded in the MSKCC grading system occurring during the intraoperative and postoperative period up to 30 days.

Immediate perioperative morbidity is defined as any complication graded in the MSKCC grading system occurring during the initial hospital stay.

The intraoperative period is defined as the period from anesthesia induction to final skin closure.

The postoperative period is defined as the period from final skin closure to the study endpoint at 6 months \pm 2 months.

Renal hypothermia will be defined as induced cooling of the kidney by externally applied ice-slush or cold crystalloid infusion via catheter of the renal pelvis or intravascularly.

Warm ischemia will be defined as no kidney cooling during renal artery occlusion.

Ischemia time will be defined as the time elapsed from renal artery occlusion by a vascular clamp to removal of the vascular clamp. Re-clamping of the vessels will be recorded as an event and total duration of ischemia recorded as the sum duration of occlusion.

Blood loss is defined as the estimate accounted from the suction device and absorptive sponges during the surgical procedure, and will be noted in the anesthesia record per institutional standard.

Intraoperative complications are defined as any complications related to either surgical or clinical aspects during the procedure, as described by the surgeon and covered by the institutional guidelines.

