13.0 CRITERIA FOR REMOVAL FROM STUDY

Patients will be withdrawn from the study if they express a desire to do so, if it is determined to be in the patient's best interest to do so, or if they do not undergo initiation of their surgical procedure as stipulated in section 12.0. Patients who are not evaluable for the study primary endpoint by failure to obtain data for the primary endpoint will be excluded from the analysis and replaced.

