14.0 BIOSTATISTICS

14.1 Primary Aim

The primary aim is to establish the difference in eGFR 6 months after surgery between the mannitol group and the placebo group. The difference will be assessed with an ANCOVA model with eGFR 6 months after surgery (+/- 2 months) as the outcome and treatment group, surgical technique, and preoperative eGFR as covariates. We will report a two-tailed p-value and a 95% confidence interval for the difference between groups. If a patient does not have an eGFR measurement between 5-7 months after surgery and has both a measurement between 3-5 months and 7-12 months after surgery, then the 6 month eGFR measurement will be linearly interpolated.

Based on historical data, patients not receiving mannitol have a mean eGFR of 60 cc/min/1.73m² 6 months after surgery. The observed correlation between the preoperative eGFR and eGFR 6 months was 0.6. The standard deviation is 14.4. Using bootstrap methods, the 75th percentile of the standard deviation was estimated to be 14.9. This inflated standard deviation was used in the sample size calculation. To detect the minimal clinical significant difference of 6 units of eGFR, a trial with 90% power and 5% alpha requires 83 patients per treatment arm. Because of the loss of power in the interim analysis, a total of 88 patients are required per treatment arm. The trial will accrue until it is anticipated that 88 patients per treatment arm will have evaluable eGFRs at 6 months. We expect that, due to drop out, this will involve accruing approximately 105 patients per treatment arm. Sensitivity analyses will be performed to assess the effect of patient withdrawal on the primary analysis.

We expect to reach our target sample size within 2 years, given that nearly 200 patients per year are eligible to enroll. We expect to enroll 8 patients per month to reach accrual in 2 years.

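### Does the mismatch between the 4-8 month outcome window and the 5-7 month interpolation trigger leave the primary eGFR value undefined?

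*Combined protocol and SAP*

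**What the plan says.** Section 14.1 specifies an "ANCOVA model with eGFR 6 months after surgery (+/- 2 months) as the outcome", so the outcome window runs from 4 to 8 months. Section 10.0 sets the same window for the visit: "Follow up visit serum creatinine measurements (6 weeks +/- 4 weeks and 6 months +/- 2 months". Section 12.0 closes the postoperative period at the same point, running "from final skin closure to the study endpoint at 6 months" with the same 2-month tolerance.

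Later in the same paragraph of Section 14.1 comes a conditional rule. For a patient who "does not have an eGFR measurement between 5-7 months after surgery and has both a measurement between 3-5 months and 7-12 months", the 6-month value is obtained by linear interpolation. Both conditions must hold: nothing at 5-7 months, and a value on each side.

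Three other places depend on having a 6-month value. Section 4.1 times the interim analysis "when 88 patients have eGFR measurements at 6 months". Section 13.0 says that patients not evaluable through "failure to obtain data for the primary endpoint will be excluded from the analysis and replaced". Section 14.1 continues accrual until 88 evaluable patients per arm are anticipated.

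**The concern.** The two windows in one paragraph do not coincide. Take a patient with no 5-7 month value but values at 4.5 and 10 months, or at 3.5 and 7.5 months. The outcome definition supplies a measured value; the interpolation sentence supplies a mixture of that value and one from outside the window. With values at 4.5 and 7.5 months there are three candidates. The text does not rank them, and it does not say which value to take when several fall within 4-8 months.

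If the gap were real in effect, the primary outcome of some patients would be left to the analyst. A value used at the interim analysis could be replaced at the final one. The count of evaluable patients, which drives replacement and the interim trigger, might also be uncertain.

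**Working it through.** **Who is affected.** Patients with no 5-7 month value, sorted by what they do have:

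| Values at (months) | Measured in 4-8 | Interpolated | Conflict |
|---|---|---|---|
| 4.5 and 10 | yes | yes | yes |
| 3.5 and 7.5 | yes | yes | yes |
| 4.5 and 7.5 | two | yes | yes |
| 3.5 and 9 | none | yes | no |
| 4.5 only, or 7.5 only | yes | no | no |

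Section 10.0 schedules one visit at 6 weeks (latest 6 + 4 = 10 weeks, about 2.3 months) and one at 6 months. Two flanking values therefore need an extra, unscheduled test, which should limit the affected group.

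**What order the wording implies.** Suppose any measured 4-8 month value came first. Interpolation could then act only on values at 3-4 and 8-12 months, and the 4-5 and 7-8 month parts of its flanking ranges would do nothing. With the order measured 5-7, else interpolated, else measured 4-8, every clause has a use.

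**The plan's own figure.** From Section 14.1: SD 14.9, correlation 0.6, difference 6, 90% power, two-sided 5%.
- Residual SD = 14.9 × √(1 − 0.6²) = 11.92.
- n per arm = 2 × (1.960 + 1.282)² × 11.92² / 6² = 82.9, so 83, as stated.
- Standard error with 88 per arm = 11.92 × √(2/88) = 1.80.

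**Weight on the out-of-window value.**
- 4.5 and 10 months: (6 − 4.5)/(10 − 4.5) = 0.273.
- 3.5 and 7.5 months: (7.5 − 6)/(7.5 − 3.5) = 0.375.
- Range: 1/7 = 0.14 (5 and 12 months) up to about 0.50 (4 and just over 8 months).

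**Per-patient gap between the rules.** The SD of the change between two visits is 14.4 × √(2(1 − r)), with r an assumption.
- r = 0.6: 12.88, times 0.273 or 0.375 = 3.5 or 4.8 units.
- r = 0.9: 6.44, times 0.273 or 0.375 = 1.8 or 2.4 units.

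**Mean shift.** Section 3.0 reports "The predicted eGFR for a typical patient 2 months after surgery was 62" in both retrospective groups, then 63 and 64 at 6 months. The slopes are (63 − 62)/4 = 0.25 and (64 − 62)/4 = 0.50 units per month. In both examples the measured value lies 1.5 months from month 6, so the rules differ on average by 1.5 × 0.25 to 1.5 × 0.50, or about 0.4-0.75 units. Interpolation moves the value up in the first example and down in the second. For times beyond 6 months this extends the slope past the range it came from.

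**Effect on the group difference.** With a share f affected in each arm, the one-SD movement is √(2f/88) × weight × SD of change.
- f = 0.05, r = 0.9, weight 0.273: √(0.10/88) × 0.273 × 6.44 = 0.06 units, or 0.03 SE.
- f = 0.20, r = 0.9, weight 0.375: √(0.40/88) × 0.375 × 6.44 = 0.16 units, or 0.09 SE.
- f = 0.20, r = 0.6, weight 0.375: √(0.40/88) × 0.375 × 12.88 = 0.33 units, or 0.18 SE.

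The last line is a pessimistic end. In Section 14.1 the 0.6 links preoperative to 6-month eGFR, across surgery. Two postoperative values a few months apart would be expected to agree more closely.

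**The case for a change.** The best case for a change is that this is the primary endpoint, where no choice should be open once data are seen, and that one paragraph would settle it. The only sensitivity analyses promised in Section 14.1 concern withdrawal, so none would show the effect of the choice. A result close to the interim or final significance level (0.0031 or 0.049) could in principle depend on it. It is true that no order is written and that no rule selects among several in-window values.

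The rest carries less weight.

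- **The obvious repair is not clearly better.** Putting any measured 4-8 month value ahead of interpolation reverses the order the text implies. With values at 4.1 and 8.1 months it would use the 4.1 month value alone, whereas the plan draws on both sides of month 6. Nothing in the documents shows that the nearest measured value estimates 6-month eGFR better than bracketed interpolation.
- **Movement between analyses would remain.** A 4.5 month value used at the interim can be displaced by a later 10 month test under interpolation. Under a nearest-value rule, a later 6.5 month test would displace it just as well. This comes from data still accruing.
- **Evaluability is not left open.** Section 13.0 ties it to having primary endpoint data, and Section 14.1 gives that endpoint its 2-month tolerance. A lone value at 4-5 or 7-8 months therefore counts. Extra accrual would arise only if measured values outside 5-7 months were refused, which is the less natural reading.

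**Conclusion.** The mismatch is real but is missing detail that an analyst can fill sensibly, and the wording already points to the order. It touches only patients with no 5-7 month value, values on both sides, and at least one of those at 4-5 or 7-8 months. Neither rule refers to treatment arm, so no directional bias is shown. The planned size of 88 per arm is untouched.

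The estimated difference would move by 0.06-0.33 units (one SD), or 0.03-0.18 SE. That rests on an assumed 5-20% of patients affected and an assumed between-visit correlation of 0.6-0.9; the documents give neither figure. Only a result almost on a significance boundary could be altered. Choosing between the two rules is a fair trade-off between a single measured value somewhat off month 6 and an estimate at month 6 that borrows a more distant value. No change to the plan follows.

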14.2 Secondary Aims

An ANCOVA model will be used to compare the difference in eGFR between treatment groups at 6 weeks (+/- 4 weeks) after surgery with postoperative eGFR as the outcome, and treatment group, surgical technique, and preoperative eGFR as covariates.

We will also use the ANCOVA on the absolute level of eGFR because this has the greatest statistical power. However, the estimate produced by ANCOVA – a mean difference in eGFR levels – is of incomplete clinical interpretability. We will therefore present estimates in two other ways for the purposes of illustrating the results in clinical terms. We will first give percentage change separately by group, along with a difference between groups. We will also report the percentage of patients in each treatment group that have postoperative eGFR less than 60 ml/min/1.73 m², as this is generally considered to represent a clinical level of kidney dysfunction.

ANCOVA will be used to compare 6 month (+/- 2 months) postoperative radionuclear scintigraphy renal scan with treatment group, baseline postoperative radionuclear scintigraphy renal scan, and randomization stratum as covariates. ANCOVA will also be used to compare estimated blood loss and ischemia time with treatment group and randomization stratum as covariates.

Multivariable logistic regression will be used to assess the difference in the rate of grade 3-5 complications between treatment groups. The multivariable model will include treatment group and randomization stratum as covariates.

We will report a two-tailed p-value and a 95% confidence interval for the difference between groups for all secondary outcomes. Summary statistics will be calculated by group for age, sex, race, BMI, serum hemoglobin, serum albumin, ASA, and Karnofsky Performance Scale.

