2.0 OBJECTIVES AND SCIENTIFIC AIMS

Primary endpoints:

- Difference in eGFR at 6 months after surgery.

Secondary endpoints:

- Difference in eGFR at 6 weeks after surgery.
- Difference in radionuclear scintigraphy renal scan at 6 months postoperatively.
- Difference in rate of grade 3-5 complications within 30 days of surgery.
- Difference in estimated blood loss.
- Difference in ischemia time.

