6.1 Subject Inclusion Criteria

- Age ≥ 18 years
- Scheduled for partial nephrectomy at MSKCC (open or minimally invasive technique) during which renal ischemia is anticipated
- Preoperative eGFR ≥ 45 cc/min/1.73m² as measured by the CKD-EPI study equation

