Mannitol solution of 12.5 gm in 200 cc of saline or placebo will be available in the OR at the time of surgery initiation. It will be administered intravenously and will be completely infused within 30 minutes prior to renal artery clamping. During the surgery, vascular occlusion will be provided using vascular bulldog or Satinsky clamp of the renal artery. If multiple primary renal vessels are encountered, selective occlusion of the vessels can be provided at the surgeon's discretion and the details regarding number of arterial vessels and number of clamped vessels recorded. Clamping or non-clamping of the renal vein will also be recorded. Patients who do not undergo clamping of the renal artery will still receive either the mannitol or placebo since kidney surgery for partial nephrectomy is intrinsically damaging to the kidney and the effects of dissection of the kidney have unknown effects on renal perfusion for which mannitol may have potential benefit.

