Any patient who does not undergo renal ischemia by vascular clamping will during their procedure will be recorded as a zero ischemia time.

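### Do skewed blood loss and zero ischemia times make ANCOVA without a rank-based check inadequate for these two secondary endpoints?

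*Combined protocol and SAP*

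**What the plan says.** Section 2.0 lists both outcomes as secondary endpoints: "Difference in estimated blood loss" and "Difference in ischemia time". Section 14.2 gives each one analysis: "ANCOVA will also be used to compare estimated blood loss and ischemia time with treatment group and randomization stratum as covariates". It then commits to reporting: "We will report a two-tailed p-value and a 95% confidence interval for the difference between groups for all secondary outcomes". No transformation is mentioned. That the raw scale is meant is an inference, though the natural one.

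The only sensitivity analyses promised are in Section 14.1 and concern a different endpoint: "Sensitivity analyses will be performed to assess the effect of patient withdrawal on the primary analysis".

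On clamping, Section 6.1 restricts entry to operations "during which renal ischemia is anticipated". Section 9.0 keeps everyone in the comparison: "Patients who do not undergo clamping of the renal artery will still receive either the mannitol or placebo". Section 12.0 fixes the value for such a patient, who "will be recorded as a zero ischemia time".

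Table 1 in Section 3.0 gives retrospective figures for minimally invasive cases. Blood loss was 150 (50, 300) without mannitol and 200 (100, 350) with it. Clamp time was 32 (23, 39) and 32 (25, 40) minutes. Ischemia occurred in 103 of 117 (88%) and 161 of 164 (98%). Continuous variables in that table were compared by the Wilcoxon test.

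**The concern.** Blood loss is typically skewed, and the plan's own background data show it. The historical comparison used medians and a rank test, whereas the trial moves to a difference in means with nothing beside it. A mean difference depends on the upper tail, which quartiles do not determine, so a few heavy bleeds could in principle decide the result.

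Ischemia time has a different irregularity, a spike at zero from unclamped patients. One mean difference then combines whether the artery was clamped with how long.

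If these features made the test unreliable, or left the result resting on a handful of patients, two reported p-values and intervals would mislead. Any robust check added later would be post hoc.

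**Working it through.** **What the trial is powered for.** The residual SD for the primary endpoint is 14.9 × √(1 − 0.6²) = 11.92. Then n = 2 × (1.960 + 1.282)² × 11.92² / 6² = 82.9, or 83 per arm, which is the plan's figure. It concerns eGFR only. No effect size or power is stated for blood loss or ischemia time.

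**Skewness in Table 1.** Quartile skewness is (Q3 + Q1 − 2 × median)/(Q3 − Q1).
- Blood loss: (300 + 50 − 300)/250 = +0.20 and (350 + 100 − 400)/250 = +0.20.
- Clamp time: (39 + 23 − 64)/16 = −0.13 and (40 + 25 − 64)/15 = +0.07.

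Blood loss is moderately right-skewed. Clamp time is close to symmetric, so the only irregularity in ischemia time is the zeros.

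**Validity of the test.** Stratum-adjusted ANCOVA was simulated with four strata and 88 or 105 patients per arm. Blood loss was taken as lognormal, gamma or square-root-normal, and the share of zeros in ischemia time as 2%, 6% or 12%. Over several sets of runs (2,500 to 6,000 trials per setting) it rejected a true null in 3.9% to 5.8% of trials. Simulation error is about ±0.7 points with 4,000 trials. Skewness and zeros do not inflate the error rate at this size.

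**Which blood-loss shape fits.** Two families were matched to Table 1.

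| Group | Table 1 quartiles | Lognormal | Gamma |
|---|---|---|---|
| No mannitol | 50 / 150 / 300 | 61 / 150 / 367 | 51 / 142 / 310 |
| Mannitol | 100 / 200 / 350 | 107 / 200 / 374 | 100 / 199 / 351 |

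The lognormal has log SD ln(300/50)/1.349 = 1.33 and ln(350/100)/1.349 = 0.93. Its upper quartile overshoots by 367/300 − 1 = 22% and 374/350 − 1 = 7%. In the first group it puts the 99th percentile at 150 × exp(2.326 × 1.328) ≈ 3,300 mL. On the log scale the Table 1 quartiles are skewed the other way (−0.23 and −0.11), so the lognormal tail is too heavy. The gamma (shape 0.81, scale 275; shape 1.44, scale 178) is much closer.

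**Influence of one heavy bleed, gamma, 105 per arm.** The half-width is 1.96 × SD × √(2/105), with SD = √shape × scale.
- No mannitol: SD = 0.90 × 275 = 247.5; half-width 67 mL.
- Mannitol: SD = 1.20 × 178 = 213.6; half-width 58 mL.

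Removing the largest bleed moves the mean difference by a median of 9 to 12 mL, about one sixth of the half-width (9/58 = 0.16; 12/67 = 0.18). The alarming figures, a 49 mL movement and a 175 mL half-width, come from the worse-fitting lognormal.

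**Power for blood loss.** At the ratio of the Table 1 medians, 200/150 = 1.33, ANCOVA against a stratified rank (van Elteren) test gives 45/35% and 69/59% under the gamma, and 18/32% and 44/56% under the lognormal. Neither test leads everywhere.

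**Ischemia time.** With mean 32 and SD (39 − 23)/1.349 = 11.9 or (40 − 25)/1.349 = 11.1, the share of variance due to zeros is p(1 − p) × 32² / [(1 − p) × SD² + p(1 − p) × 32²]. That is 13–14% at p = 2% and 47–50% at p = 12%. For an assumed 5-minute shift, ANCOVA/rank power is 79/80% to 84/86% at 2% unclamped, 52/62% to 54/68% at 12%, and 85/83% to 91/89% when all are clamped. If only the unclamped rate differs (2% against 12%), ANCOVA has 37–40% and the rank test 23%.

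**The case for a change.** The strongest case for a second analysis is an additive effect. If mannitol added 50 mL to every patient's blood loss, the rank test would be well ahead even under the gamma (73% against 31%, and 62% against 40%). The quartiles do not fix the tail, so heavier bleeding than the gamma implies cannot be excluded. At the 1.33 ratio the two tests reach different verdicts on significance in 16–25% of trials. Section 14.2 also calls the mean difference in eGFR hard to interpret clinically and adds two further summaries there, but none here.

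These facts stand. They concern efficiency under particular alternatives, on endpoints for which no power is claimed; they do not make the ANCOVA result wrong. Disagreement is expected between two tests of moderate power aimed at different quantities. For the same reason, setting the mean-difference half-width (58–175 mL) beside that of the rank-based shift (38–44 mL) compares two estimands. The risk of choosing between methods after unblinding arises when a plan leaves the method open. This plan names one.

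On ischemia time, a rank test that keeps the zeros also merges clamping with duration, so it would not separate the two. Dropping the unclamped would: but clamping happens after randomization, so that comparison would no longer be a randomized one. Zero minutes is the patient's actual value, and the rule is set in advance. The number unclamped per arm is informative, and it can be read from data the trial already records. The 12% rate is a poor guide here: it comes from the retrospective no-mannitol group, whereas this trial enrols only where ischemia is expected. At 2% the two tests differ by 1 to 2 points of power.

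**Conclusion.** Not a defect. The plan names a valid, prespecified comparison of means for two secondary endpoints that do not drive the sample size, and the error rate holds near 5% (3.9% to 5.8% in simulation) despite skewness and zeros. Under the shape that best matches Table 1, one extreme bleed moves the blood-loss estimate by about 9 to 12 mL against a half-width of 58 to 67 mL, and ANCOVA is the stronger test for a proportional effect. A rank analysis would gain power in some settings, lose it in others, and leave the mixing of clamping and duration unresolved. It is a reasonable optional extra; its absence is not an error.

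This rests on assumed distributions fitted to retrospective, minimally invasive cases, while the trial also enrols open cases. Assuming blood loss 1.5 times higher in open cases left the null and ratio-effect results within 2 points. The size of any influence from a few bleeds would grow if the true tail were much heavier than the gamma.
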